STUDY PROTOCOL WITH STATISTICAL ANALYSIS PLAN

Official title:

Physical Therapist as Primary Assessor for Patients With Knee Pain in Primary Care

NCT number: NCT03715764

The Regional Ethical Review Board in Gothenburg approved the study 2013-03-15, reference numbers: 979–12, T674–13, T497–14, T791–15.

Document date: Protocol published and released on clinicaltrial.gov 2018-10-22.

Study Description

Brief Summary:

In order to manage the future increase in osteoarthritis consultation, patients with osteoarthritis could be assessed by a physical therapist first, so that other patients with more severe conditions could get faster access to a primary care physician. In Swedish primary care, physicians and physical therapists are primary assessors for patients with suspected knee osteoarthritis. However, it is unclear if there are any differences between these managements in improving health-related quality of life (HrQoL), pain, physical function and self-efficacy.

There is a limited amount of studies about the impact on HrQoL, pain intensity, self-efficacy and physical performance in patients with knee pain being assessed and evaluated by a physical therapist as a primary assessor.

The overall purpose of this study is to evaluate the effects on self-rated HrQoL, pain intensity, self-efficacy and physical performance with either a physical therapist or a physician as primary assessor for patients with knee pain within primary health care.

Problem statements

Which effect does a clinical pathway with a physical therapist as primary assessor for patients with knee pain...

... have on self-rated HrQoL compared with a physician as primary assessor?

... have on self-rated pain intensity compared with a physician as primary assessor?

... have on physical performance compared with a physician as primary assessor?

... have on self-efficacy compared with a physician as primary assessor?

It is expected that this study will show the effects of two different primary assessors for patients with knee pain consulting primary health care. The results could clarify which profession that is most appropriate to be the primary assessor for patients with knee pain in primary health care.

Detailed Description:

Patient Recruitment Recruiters: Primary care centers.

Screening procedure

Nurses at the primary care centers will get information about the study and the screening protocol from the data collector and project leader. There will be contact persons at each recruiting unit that will be responsible for the protocols and to contact the data collector when a patient fulfills all the criteria for participation. The project leader will have regular contact with the contact persons at the recruiting units. All screening protocols will be sent to the data collector. All participants will get orally and written information about the study from the data collector, and patients will provide written informed consent.

Randomization

Using a computer-generated list of random numbers, participants will be randomly assigned to being assessed, diagnosed and treated either by a physiotherapist or a physician first. A project coordinator is included among the health care providers in the study, but will not be involved in the screening procedure nor the data collection. The project coordinator will manage the sequence generation, allocation concealment, enrolment and assignments of participants and keep the concealed randomization scheme and sequentially numbered, sealed envelopes in a locked cupboard (in the same building where the enrolment will be), only available for the project coordinator. The project coordinator reveals the allocation to the participant shortly after the baseline measurement and to the health care providers.

Participants and health care providers in both groups will be aware of the allocated group, whereas data collector, data analyst and statistician will be kept blinded of allocation until completion of all outcome assessments.

The blinded data collector and analyst (is a physical therapist) whom is not involved in assessing diagnosing and treating patients with knee osteoarthritis while the study is conducted.

Data Collection

Measurements will be collected at baseline (before randomization), at 3-, 6-, and at 12 months follow up. All data will be coded and managed according to the Data Protection Act (1998:204), which means that all data will be confidential, and no unauthorized will have access to the patient registry. The results will be presented at group level; therefore, no individual information can be identified. Data will be saved for at least 10 years to enable audit.

Sample size

To detect a minimal clinical improvement in health-related quality of life of 0.121(SD 0.2) on the EQ5D-index, with a two-sided 5% significance level and a power of 80%, a sample size of 50 patients per group will be necessary, given an anticipated dropout rate of 14%.

Statistical analysis

Data will be analyzed descriptively and presented as numbers and percent, mean and standard deviation or median and 25th to 75th percentiles. The primary outcome will be mean change in HrQoL (EQ5D-index and EQ5D-scale) and secondary outcomes will include mean change in pain intensity (VAS), physical performance (30CST) and self-efficacy (ASES-S). The changes in scores for the outcomes will be constructed by calculating raw differences between baseline and the follow ups.

For group comparison the X²-test will be used for nominal data and Fischer's exact test for small numbers, parametric student t-test for continuous variables and Mann-Whitney's test for ordinal data and at skewed distributions. Statistical analysis will be made in SPSS Windows and the analysis will be applied with intention-to-treat (ITT). The level of significance will be p< 0.05.

Study Design

Study Type: Interventional (Clinical Trial)

Actual Enrollment: 69 participants. Anticipated enrollment, 100 participants.

Allocation: Randomized

Intervention Model: Crossover Assignment

Masking: Double (Investigator, Outcomes Assessor)

Primary Purpose: Treatment

Arms and Interventions

Intervention: Physical therapy assessment

Patients allocated to the intervention group will be assigned to an assessment and evaluation by a physical therapist. If they are diagnosed with knee osteoarthritis they will get an offer to participate in a patient education program and physical training with an individualized exercise program made by a physical therapist. Patients will be offered individual treatment if they decline to participate in the education program, or if they have another diagnosis than osteoarthritis. Anytime after the first assessment by the physical therapist, the patient will be able to contact a physician if they want to.

Control: Physician assessment

Allocation to the control group will involve an assessment and evaluation made by a physician. Further measures will then be determined by attending physician and the procedures that might get included are drug prescriptions, referral to x-ray examination, referral to a physical therapist or another health care provider. Anytime after the first assessment by the physician, the patient will be able to contact a physical therapist if they want to, even though if they have not been referred by the physician.

Outcome Measures

Primary Outcome Measures

Change from health related quality of life (HrQoL) at 12 months

[Time Frame: Baseline (before randomization) to 12 months]

A Swedish version of Euroqol-5 dimensions-3 levels (EQ5D-3L) will be used to assess perceived self-rated health-related quality of life. EQ5D-index respectively EQ5D-VAS will be presented. The questionnaire contain five dimensions and results in an index ranging from -0,549 to 1 using the UK tariffs. An index of 1 indicate full health. The EQ5D-VAS is a visual analogue scale ranging from 0 to 100, where 0 is worst imaginable health state and 100 is best imaginable health state.

Secondary Outcome Measures

Change from pain intensity at 12 months

[Time Frame: Baseline (before randomization) to 12 months]

The mean pain intensity (over the past month) will be measured by a visual analogue scale (VAS) ranged from 0 which will correspond no pain and 100 the worst imagined pain.

Change from physical function at 12 months

[Time Frame: Baseline (before randomization) to 12 months]

Physical performance will be measured with 30 seconds chair stand test (30CST). Number of stands will be counted.

Change from self-efficacy at 12 months

[Time Frame: Baseline (before randomization) to 12 months]

Self-efficacy will be assessed with Arthritis Self-Efficacy Scale-Swedish version (ASES-S). Each question range from 10-100, where 10 is very insecure and 100 is very confident. The questionnaire consists three subscales in how patients are experiencing their 1) pain, 2) physical function, 3) other symptoms. Each subscale results in a mean score ranging from 10 to 100 where 10 means very insecure and 100 means very confident.

Other Outcome Measures:

Demographic data

[Time Frame: Baseline (before randomization)]

Demographic data such as age, sex, origin, marital status (married/living with partner or single household), education, self-reported work status and pain duration, will be included in a standardized questionnaire. Patients' body weight and height will be measured to calculate a Body Mass Index (BMI).

Eligibility Criteria

Ages Eligible for Study: 38 Years and older (Adult, Older Adult)

Sexes Eligible for Study: All

Accepts Healthy Volunteers: No

Inclusion Criteria:

Age >38 years old, knee pain most of the days the last month, crepitus on active motion, morning stiffness, duration less than 30 minutes. The patient has to understand the Swedish language to follow test instructions and to complete the self-administered questionnaires.

Exclusion Criteria:

Already been assessed/diagnosed by a healthcare provider for current knee pain, knee pain due to a traumatic cause, other rheumatic or systemic diseases, severe somatic or mental disease, pregnancy.

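### The promised blinding of the data analyst and statistician stops at the last outcome assessment, so the plan permits the primary analysis to be done with the arms known

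*Combined protocol and SAP*

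**What the plan says.** All references are to the combined protocol and SAP.

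- **Randomization, end of the blind.** The "data collector, data analyst and statistician will be kept blinded of allocation until completion of all outcome assessments". One end point serves all three roles.
- **Randomization, who the analyst is.** "The blinded data collector and analyst (is a physical therapist", and this person takes no part in the care of knee osteoarthritis patients while the study runs. The statistician's profession is not given.
- **Randomization, what is compared.** Participants are "assessed, diagnosed and treated either by a physiotherapist or a physician first".
- **Data Collection.** "Measurements will be collected at baseline (before randomization), at 3-, 6-, and at 12 months follow up". Data are to be coded, but this is stated as a confidentiality measure under data protection law, not as masking of group labels.
- **Statistical analysis.** "The primary outcome will be mean change in HrQoL (EQ5D-index and EQ5D-scale") with no order between the two measures. The tests are "parametric student t-test for continuous variables and Mann-Whitney's test for ordinal data and at skewed distributions". ITT is named without a rule for missing data.
- **Study Design.** "Masking: Double (Investigator, Outcomes Assessor"). The analyst and statistician are not named there.
- **Outcome Measures.** The primary time frame is baseline to 12 months, and both the EQ5D index and the EQ5D VAS are to be presented.

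No section provides for analysis with coded arms, for a database lock, or for sign-off of analysis decisions before allocation is revealed.

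**The concern.** Completion of the last assessment is a natural end to the blind for a data collector, whose work then stops. For an analyst and a statistician, the main work starts there. A reader who sees that these two roles are blinded will assume that the analysis is protected, and the sentence does not promise that.

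This matters more here than in many trials. The study asks which profession should see patients with knee pain first, and the analyst belongs to one of the two. No intent need be supposed. If the distribution is borderline, or patients with missing 12-month data must be handled one way or another, an analyst who knows the arms can see which choice favours which profession. At stake is the credibility of a comparison between professions, which is cheap to protect in advance and hard to defend afterwards.

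**Working it through.** **1. Timing.** The last measurement is at 12 months (Data Collection). The primary outcome is change to 12 months (Outcome Measures). The primary comparison needs the 12-month data, so it cannot be run until all assessments are complete, which is when the promised blind expires. An analysis with known arms would comply with the plan as written.

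**2. What is fixed and what is open.**

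| Item | Status in the plan |
|---|---|
| Primary time point | Fixed: 12 months |
| Form of the outcome | Fixed: raw change from baseline |
| Significance level | Fixed: 0.05 |
| Analysis principle | Fixed: ITT |
| t-test or Mann-Whitney | Open: Mann-Whitney is used when the distribution is skewed, with no criterion for skewness |
| Missing data under ITT | Open: no rule, with 14% dropout anticipated |
| EQ5D index or EQ5D VAS | Both are presented; which to emphasise is open |

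**3. The plan's own figure.** The sample size does not bear on this point, but it reproduces. With difference 0.121, SD 0.2, two-sided 5% and 80% power:

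n = 2 × (1.960 + 0.842)² × 0.2² / 0.121² = 2 × 7.85 × 0.04 / 0.01464 ≈ 42.9, so 43 per group. With 14% dropout, 43 / 0.86 = 50, as stated.

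**4. An upper limit for steering.** The documents give no figure for this, so the inputs below are assumptions.

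- Analysed per arm: 43 (50 × 0.86), and about 30 (actual enrolment 69 / 2 × 0.86 = 29.7).
- No true difference; two measures, log-normal with sigma 0.8, correlation 0.3 or 0.7; 5000 runs per setting.
- A run counts if any permitted choice gives two-sided p < 0.05 in one chosen direction. The reference rate is 5% / 2 = 2.5%.

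| Freedom taken | Rate in one chosen direction |
|---|---|
| One test and measure fixed in advance (nominal) | 2.5% |
| Either test, one measure | about 3 to 4% |
| Either test, either measure | about 5.5 to 7% |

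**5. Which rate is relevant.** Counting significance in either direction gives about 6 to 7% for either test on one measure, and about 10 to 13% for either test on either measure, against 5%. Those rates do not measure this gap. A two-sided t-test or Mann-Whitney p-value is the same whether the arms are called A and B or by their names, so coding the arms would leave them unchanged. They describe multiplicity and the open choice of test. What knowledge of the arms adds is the ability to pick by direction, which is why the table counts one direction only.

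**The case against.** The strongest reply is that this is a modest gap in wording.

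- **Disclosure is not stated.** A reader might infer that the arms are revealed before the analysis begins. The text does not say so. It sets a minimum duration for the blind and is silent on what follows. This stands: the defect is that analysis with known arms is permitted, not that it is planned or took place.
- **The blind does useful work.** A reader might conclude that it is worthless for the analyst. It is not. The same person collects the outcomes, including the observed chair stand test, and is masked throughout that work and any data handling done during follow-up. This person's exclusion from the care of knee osteoarthritis patients is a further safeguard. Neither covers decisions taken at analysis.
- **The latitude is limited.** Time point, change score, ITT and significance level are set, the sample size rests on the EQ5D index, and both EQ5D measures must be presented. Suppressing one measure would breach the plan, so the freedom there is one of emphasis. On clearly skewed data the plan already selects Mann-Whitney, and picking the t-test would also be a breach. The real freedom is in borderline distributions, so the simulated rates overstate it.
- **Profession.** It is documented for the analyst only. Nothing can be said about the statistician's.

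These replies reduce the size of the point. None of them supplies blinding for the primary analysis.

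**Conclusion.** The point holds in a limited form. The plan promises no blinding of the analyst and statistician during the primary analysis, the analyst comes from one of the two professions compared, and a few data-dependent decisions remain open.

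As an upper limit, the chance of a false-positive result in one chosen direction is about 3 to 4% with a free choice of test on one measure, and about 5.5 to 7% with a free choice of test and measure, against 2.5%. This rests on assumed log-normal data, on assumed correlations of 0.3 to 0.7, and on the favourable option always being taken. The effect of open missing-data handling is not included. The rates are not the error that coding the arms would remove, since an analyst with coded groups could still pick the smaller p-value without knowing whom it favours. Nor are they evidence that any selection occurred.

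The gap does not undermine the design. It should be closed because closing it costs almost nothing.

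**What to change.** Replace the single end point in the Randomization section with one for each role, for example:

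> The data collector will remain blinded until every outcome assessment is complete. The data analyst and the statistician will work with groups coded A and B until the database is locked and the choice of test, the handling of missing data, and the analyses of the primary and secondary outcomes are final. The project coordinator will hold the code.

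Because one person is both data collector and analyst, the later end point applies to that person. The project coordinator already keeps the randomization scheme and takes no part in data collection, so no new role is needed. If the analysis has already been done, the report should state whether the arms were known at the time.

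The cost is a coded group variable in the SPSS file and a short delay before the arms are revealed. No extra staff, patients or visits are needed, and the same analyst can continue.

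Coding the arms does not settle the skewness criterion, the missing-data rule or the order of the two EQ5D measures. Those need their own rules in the Statistical analysis section.

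### EQ5D-index and EQ5D-VAS are both primary at p<0.05 with no rule for combining them, so the 5% level is not secured

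*Combined protocol and SAP*

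**What the plan says.** The Statistical analysis section defines the primary endpoint by two measures: "The primary outcome will be mean change in HrQoL (EQ5D-index and EQ5D-scale"). The same section sets one general threshold, "The level of significance will be p< 0.05", and assigns tests by type of variable (t-test, or Mann-Whitney for ordinal or skewed data).

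Under Primary Outcome Measures there is one entry, "Change from health related quality of life (HrQoL) at 12 months", so the primary time point is fixed. On the two measures that entry says only "EQ5D-index respectively EQ5D-VAS will be presented". The names differ (EQ5D-scale in one place, EQ5D-VAS in the other), but the outcome section makes it reasonable to read them as the same 0 to 100 scale.

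The Sample size section uses the index alone: "0.121(SD 0.2) on the EQ5D-index, with a two-sided 5% significance level", with 80% power and 14% dropout, from which "a sample size of 50 patients per group will be necessary".

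The document contains no testing order, no division of alpha, no requirement that both measures be significant, and no statement that one of them decides.

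**The concern.** The index (-0.549 to 1) and the VAS (0 to 100) are different variables and need two tests. With both called primary and one unadjusted level, at least three success rules fit the text: the index decides, either measure suffices, or both are required. They differ in error rate and in power.

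If either suffices, the chance of a false positive primary result exceeds 5%. If both are required, the error is controlled but power falls below the 80% the trial was sized for. If the measures disagree, the plan has no defined primary answer, and the rule could be picked once the results are known. A significant VAS with a null index could be reported as a positive primary outcome without departing from the plan. The Brief Summary expects the results to help decide which profession should assess these patients first, so the ambiguity bears directly on the trial's main conclusion.

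**Working it through.** **Inputs from the document.** Difference 0.121 and SD 0.2 on EQ5D-index, two-sided alpha 0.05, power 80%, dropout 14%, 50 per group (Sample size); two primary measures and p<0.05 (Statistical analysis); 12 months (Primary Outcome Measures).

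**Assumed inputs.** The correlation r between the two test statistics is not given, so r = 0 to 0.9 is shown. For the VAS the document gives no target difference, SD or power. Where power is needed, 80% is assumed, equal to the index.

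**Step 1: reproduce the planned sample size.**

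n per group = 2(1.960 + 0.842)² / (0.121/0.2)² = 2(2.802)² / (0.605)² = 42.9, so 43 evaluable per group. Allowing for dropout, 43/0.86 = 50. This matches the plan exactly, for one test of the index at the full two-sided 5%.

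**Step 2: either measure counts, no true effect.**

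False-positive rate = 1 − P(|Z₁| < 1.96 and |Z₂| < 1.96), with (Z₁, Z₂) bivariate normal with correlation r. At r = 0 this is 1 − 0.95² = 9.75%. A simulation of t-tests with 43 per group (200,000 trials per value of r) gave 9.6%, 9.5%, 9.0%, 8.3%, 7.8% and 7.0% for the six correlations below, in agreement with the exact values.

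**Step 3: both must be significant.**

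Under the null, the joint rejection rate cannot exceed that of either test, so it is at most 5%. For power, each statistic is given mean 1.960 + 0.842 = 2.802 (80% power each). At r = 0 joint power is 0.80 × 0.80 = 64%.

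**Step 4: exactly one significant.**

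Since each test has 80% power, this probability is 2 × (0.80 − joint power). At r = 0 it is 2 × (0.80 − 0.64) = 32%.

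| Assumed r | Either counts: false-positive rate | Both required: joint power | Exactly one significant |
|---|---|---|---|
| 0 | 9.75% | 64.0% | 32.0% |
| 0.3 | 9.51% | 66.6% | 26.8% |
| 0.5 | 9.07% | 68.7% | 22.6% |
| 0.7 | 8.35% | 71.3% | 17.4% |
| 0.8 | 7.81% | 72.9% | 14.2% |
| 0.9 | 7.04% | 75.0% | 10.0% |

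**Step 5: index alone decides.** One test at two-sided 0.05 has a 5% error and needs the 43 evaluable, or 50 enrolled, per group of Step 1.

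**Step 6: splitting alpha, for comparison.** Testing each measure at 0.025 would need 52 evaluable per group for the index, or 52/0.86 = 60.5, so 61 enrolled. With the planned 43 evaluable per group, index power falls from 80.1% to 71.4%.

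**The case against.** The strongest reply is that the plan already points to the index. It is named first in both places, it alone has a target difference, SD and power, and the VAS is only to be presented, which is reporting language. On that reading the 5% level holds, and what is missing is a sentence confirming it. The plan nowhere says that either measure suffices, and it claims no family-wise control. The hint is real, but sizing a trial on one measure is not a testing rule. The analysis section gives the VAS equal primary status and exempts neither measure from testing at p<0.05.

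A second reply is that two self-ratings from one questionnaire are likely to be correlated, so 9.75% is the worst case. That stands as far as it goes: at r = 0.7 to 0.9 the excess over 5% is 3.4 to 2.0 percentage points. It shrinks the inflation without removing it, and it leaves the rule undefined.

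Third, the joint-power and discordance figures rest on an assumed 80% power for the VAS. They are illustrative and should be read that way. They also describe the planned trial. The Study Design section reports 69 enrolled against 100 anticipated. With equal groups and 14% dropout (34.5 × 0.86 = about 30 per group), index power on the plan's own difference and SD is about 64%, so requiring both would leave joint power at or below that.

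Fourth, the data analyst and statistician stay blinded until all outcome assessments are complete. That limits choosing a rule after seeing results but does not replace fixing it beforehand. Finally, leaving t-test or Mann-Whitney to depend on skewness is a separate open choice that this point does not settle.

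**Conclusion.** The concern holds. Two unranked primary measures share one unadjusted 5% level with no decision rule, so the level is not secured. It would hold if the index alone decided or if both measures were required, but the plan states neither.

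Under an either-counts rule the false-positive rate at 12 months is 7.0% to 9.75% for r from 0.9 to 0, and it exceeds 5% at any correlation short of perfect. That range rests only on the assumed correlations. The power loss and the risk of a split result also depend on the assumed VAS power. The sample-size arithmetic is correct for the index alone. The 3- and 6-month visits are not counted as further primary tests, because the outcome section fixes 12 months.

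This must be fixed, because it concerns what counts as success for the trial.

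**What to change.** State in the Statistical analysis section that the single primary outcome is change in EQ5D-index from baseline to 12 months, tested at two-sided 0.05, and list EQ5D-VAS as secondary. Edit Primary Outcome Measures to match and use one name for the VAS throughout. This follows the plan's own sample size and time point.

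If both measures must stay primary, test in fixed order: the index at 12 months first at two-sided 0.05, and the VAS at the same level only if the index is significant. This holds the family-wise error at 5% without splitting alpha.

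Either version costs one sentence and a matching edit, with alpha and the planned 50 per group unchanged. The price is that the VAS can no longer carry the primary claim alone. Because actual enrolment is already reported, the change should be dated and made before unblinding. If allocation or results are already known, the report should say that the choice was made afterwards.

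### The primary comparison tests raw change without baseline adjustment; ANCOVA on the same data would usually be more precise, by an amount the documents do not settle

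*Combined protocol and SAP*

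**What the plan says.** The Statistical analysis section names the endpoint, "The primary outcome will be mean change in HrQoL (EQ5D-index and EQ5D-scale", and says how it is formed: "The changes in scores for the outcomes will be constructed by calculating raw differences between baseline and the follow ups". For the group comparison it prescribes "parametric student t-test for continuous variables and Mann-Whitney's test for ordinal data and at skewed distributions". No regression, ANCOVA, mixed model or baseline covariate appears anywhere in the document. Outcome Measures sets the primary time point at 12 months.

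The covariate needed for adjustment is already collected. Under Data Collection: "Measurements will be collected at baseline (before randomization", with follow-up at 3, 6 and 12 months.

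The Sample size section plans on an improvement in "health-related quality of life of 0.121(SD 0.2) on the EQ5D-index", two-sided 5% significance, 80% power and 14% dropout, giving 50 per group. It does not say whether 0.2 is the SD of a single score or of the change. Study Design reports "Actual Enrollment: 69 participants" against 100 anticipated.

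**The concern.** A t-test on raw change is an ANCOVA in which the baseline coefficient is held at 1. Both analyses target the same mean difference under randomisation, so the target of 0.121 is unaffected. The true slope is often below 1, through measurement error and regression to the mean. The change score then over-corrects for baseline, carries extra variance, and leaves the estimate exposed to chance baseline imbalance. No stratification is described, so nothing else in the design limits that imbalance.

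What is at stake is precision, in a trial that enrolled about two thirds of its target and already holds the data needed to recover some of the loss.

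The rank-test fallback is a related but separate weakness. The plan gives no rule for deciding that a distribution is skewed, so the primary test could be chosen after looking at the data. A Mann-Whitney test also does not test or estimate a difference in mean change, which is the declared primary quantity.

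**Working it through.** **Inputs from the document.** Difference 0.121; SD 0.2; two-sided 5%; power 80%; dropout 14%; 50 per group planned; 69 enrolled.

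**Assumptions (not in the document).** Baseline-to-12-month correlation rho of 0.3, 0.5, 0.7 or 0.8; ratio k of the 12-month SD to the baseline SD of 1, 1.25 or 0.8; 1:1 split of completers.

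**1. The plan's own figure.** n per group = 2 × (1.960 + 0.842)² × 0.2² / 0.121² = 42.9, so 43; 43 / 0.86 = 50. The stated sample size reproduces.

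**2. Completers at actual enrolment.** 69 × 0.86 = 59.3, taken as 59 (30 and 29).

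**3. Variance ratio with equal variances (s² at both times).** Var(change) = 2s²(1 − rho). Var(ANCOVA) = s²(1 − rho²). Ratio = (1 + rho)/2.

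**4. Power for 0.121.** Noncentral t, 57 df for change and 56 df for ANCOVA. Reading A takes 0.2 as the SD of change, so the ANCOVA SD is 0.2 × √((1 + rho)/2). Reading B takes 0.2 as the SD of a single score, so the SD of change is 0.2 × √(2(1 − rho)) = 0.237, 0.200, 0.155, 0.126, and the ANCOVA SD is 0.2 × √(1 − rho²).

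| rho | Variance ratio | Saving | A: change | A: ANCOVA | B: change | B: ANCOVA |
|---|---|---|---|---|---|---|
| 0.3 | 0.65 | 35% | 62.7% | 80.8% | 48.8% | 66.8% |
| 0.5 | 0.75 | 25% | 62.7% | 75.1% | 62.7% | 75.1% |
| 0.7 | 0.85 | 15% | 62.7% | 69.7% | 83.9% | 89.2% |
| 0.8 | 0.90 | 10% | 62.7% | 67.2% | 95.1% | 96.7% |

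Under reading A the 95% CI half-width is 0.104 for change, against 0.084, 0.090, 0.096 and 0.099 for ANCOVA. At rho 0.5, 59 completers under ANCOVA carry about the information of 59 / 0.75 = 79 under raw change.

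**5. Unequal variances.** Ratio = k²(1 − rho²) / (1 + k² − 2·rho·k). It equals 1 only when the true slope, rho × k, is 1.

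| k | rho 0.3 | rho 0.5 | rho 0.7 | rho 0.8 |
|---|---|---|---|---|
| 1.25 | 0.78 | 0.89 | 0.98 | 1.00 |
| 0.8 | 0.50 | 0.57 | 0.63 | 0.64 |

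**6. Small-sample cost.** The formulas in steps 3 to 5 leave out the variance cost of estimating the slope. It is roughly 1/(n − 4) = 1/55, or 1.8%, at n = 59. Simulation with 30 and 29 per group agrees: at k = 1.25 and rho 0.8 ANCOVA's variance is about 2% larger than that of the change score; at k = 1.25 and rho 0.7 the two are about equal; at k = 1 and rho 0.8 the saving is a little over 8%, not 10%.

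**7. Chance imbalance (equal variances).** A one-standard-error baseline difference shifts the change-score estimate by (1 − rho) × SE of the baseline difference. Reading B: SE = 0.2 × √(1/30 + 1/29) = 0.052, so the shifts are 0.036, 0.026, 0.016 and 0.010. Reading A: SE = 0.052 / √(2(1 − rho)), so the shifts are 0.031, 0.026, 0.020 and 0.016. Overall this is 0.010 to 0.036, or 9% to 30% of 0.121.

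**The case against.** The strongest reply is that nothing here is an error. The endpoint is defined as change and tested as change, the test is unbiased, and the sample size reproduces on its own inputs. Every figure for the gain rests on a correlation and an SD ratio that the document does not give; across the assumed range the saving runs from about 50% to none, and in the least favourable case ANCOVA is about 2% worse. All of that stands. It limits what can be said about size, but the gain remains the usual result.

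Three further points are fair:

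- The imbalance figures are not an additional harm. With equal variances, the squared shift divided by the change-score variance is (1 − rho)/2, exactly the saving already reported. They show the same loss in the units of the endpoint.
- The low power comes mainly from under-enrolment. ANCOVA offsets part of the shortfall; the choice of test did not cause it.
- The Mann-Whitney weakness would exist without any argument for ANCOVA, and the power figures above apply only to the t-test.

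Timing may also limit the remedy. Actual enrolment is already reported, and the Randomization section says the "data analyst and statistician will be kept blinded of allocation until completion of all outcome assessments". The document does not show whether that point has passed.

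**Conclusion.** The concern holds as a matter of efficiency, not validity. The planned raw-change t-test gives up precision whenever the true baseline slope is appreciably below 1, and the plan includes no adjustment although the baseline is measured before randomisation.

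Confidence is high in the usual direction and low in the size. With equal variances and rho from 0.3 to 0.8, the variance saving is 35% to 10%, less about 2% for estimating the slope. The power gain with 59 completers is about 18 to 4 percentage points under reading A and 18 to 2 under reading B. If the 12-month SD is 1.25 times baseline, the gain shrinks to nothing by rho 0.8. These figures assume 14% dropout and near-equal groups.

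The undefined skewness trigger, and the mismatch between a rank test and mean change, also stand as a point without a calculated size. The change should be made, but the trial's conclusions would not be invalid without it.

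**What to change.** If allocation is still blinded, amend the Statistical analysis section, with a date, as follows:

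- **Primary analysis:** linear regression of the 12-month value on randomised group and the same measure at baseline, fitted separately for EQ5D-index and EQ5D-scale.
- **Secondary outcomes:** the same model for pain VAS, 30CST and each ASES-S subscale, each with its own baseline.
- **Reporting:** adjusted mean difference with 95% CI. If residuals are skewed, use robust or bootstrap standard errors in place of the switch to Mann-Whitney, so that the mean difference stays the target.
- **Sensitivity analyses:** the planned t-test on raw change and the Mann-Whitney test.

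If allocation has already been revealed, keep the planned test as primary and report ANCOVA beside it, labelled post hoc.

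The cost is a few lines of SAP text, a standard SPSS procedure and one degree of freedom per model. No new data are needed. Because this changes the primary analysis after enrolment, the amendment should record the blinding status on its date.
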